### **5.2.2.3 Lead-in Population for Safety Analysis**

The first eight patients from each arm will be enrolled as the lead-in population. Safety analysis will be performed with this population and will be analyzed on a rolling basis. Weekly conference calls with all the sites will be held to determine if any of these first 8 patients have experienced a dose limiting toxicity, DLT, (described below) to evaluate the safety of the combination as well as the safety of administering Pembrolizumab before surgery. Safety analysis will be considered complete for each arm at four weeks after the eighth patient has finished CRT. Patients will continue to be enrolled past the initial safety cohort, but if at any time, safety analysis reveals >2 out of the 8 patients in the safety cohort have developed a DLT, then no further patient may be enrolled to that arm due to excess toxicity with this combination. If the safety event occurs prior to surgery only, than the pre-surgery dose of Pembrolizumab will be discontinued for the following patients but the trial will continue with adjuvant treatment only.

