## 1.0 TRIAL SUMMARY

Abbreviated Title	Adjuvant HNC anti-PD1 chemoradiation phase II study
Trial Phase	Phase II
Clinical Indication	High and Intermediate risk resected HNC
Trial Type	2 arm, non-randomized
Type of control	Historical
Route of administration	IV
Trial Blinding	None

Treatment Groups	High risk and Intermediate risk
Number of trial subjects	80
Estimated enrollment period	3 years
Estimated duration of trial	8 years (5 years disease free survival (DFS) + 3-year enrollment period)
Duration of Participation for subjects	5 years

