### 8.1.4 Accrual Rate

At the University of Cincinnati, we see approximately 150 new cases of surgically treatable (oral cavity, larynx, hypopharynx) stage III/IV HNSCC per year. Of those, approximately 100% oral cavity, > 50% larynx, and 50% hypopharynx receive surgical resection and about 40%

require adjuvant therapy. We therefore, expect to accrue approximately 1-2 patients per month at UC. Per discussions with our other sites (OSU, Univ of Louisville, MUSC, USCD and Univ of Mich, MD Anderson) we expect to add ~ 1-2 patients a month from each as well. Therefore, we expect enrollment for this phase II study to be completed within 1 year based on 80 patients.

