## 8.2 Statistical Analysis Plan

### 8.2.1 Safety Endpoints

The safety endpoints are all adverse events graded from 1 to 5 described in Section 7.

The Lead-in population will be assessed for DLTs as described in section 5.2.2.3.1.

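### The only numeric toxicity stopping rule counts DLTs in the first eight patients per arm; about 32 of 40 patients per arm fall outside any pre-set boundary, although enrolment continues while the lead-in is pending

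*Combined protocol and SAP*

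**What the plan says.** Section 5.2.2.3 defines the cohort: "The first eight patients from each arm will be enrolled as the lead-in population". The weekly review looks at the same patients: "Weekly conference calls with all the sites will be held to determine if any of these first 8 patients have experienced a dose limiting toxicity". The boundary closes enrolment in the arm concerned: "safety analysis reveals >2 out of the 8 patients in the safety cohort have developed a DLT, then no further patient may be enrolled". A DLT (5.2.2.3.1) is an adverse effect that the investigator attributes to pembrolizumab and that delays surgery, radiation or cisplatin beyond stated limits. The lead-in is complete four weeks after the eighth patient finishes chemoradiation, but enrolment does not wait: "Patients will continue to be enrolled past the initial safety cohort, but if at any time, safety analysis reveals >2 out of the 8 patients".

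Section 4.2.3.1 gives the same 2-in-8 threshold. The statistical section adds only this: "The Lead-in population will be assessed for DLTs as described in section 5.2.2.3.1". No target rate, unacceptable rate or operating characteristic is stated.

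Three other provisions reach later patients. A DLT ends pembrolizumab for that patient (5.2.2.3.1). Incidence or severity of adverse drug reactions is a ground for early termination (5.9, item 3). The DSMB regularly receives the frequency and severity of adverse events (10.6.2). The last two carry no number, and the DSMB is advisory.

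On accrual, Section 8.1.4 says "we expect enrollment for this phase II study to be completed within 1 year based on 80 patients", while Section 1.0 gives a trial duration of "8 years (5 years disease free survival (DFS) + 3-year enrollment period").

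**The concern.** Section 4.2.3.1 says that pembrolizumab had not been explored clinically with cisplatin and radiation, and safety is the first primary objective (3.1). Yet the numeric rule uses about one fifth of the patients in an arm (8 of 40). A DLT in patient 9 is outside the count even if it occurs while the lead-in is still open. Eight patients give a weak screen: a moderately high DLT rate can pass by chance, and after that no pre-set number tells the investigators or the DSMB when accumulating DLTs should close the arm. Because enrolment continues, a sizeable share of the trial may be dosed by the time the lead-in is complete.

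**Working it through.** The plan gives no operating characteristic for this rule, so there is no figure of its own to reproduce.

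**Inputs from the documents.** 8 lead-in patients per arm, stop at 3 or more DLTs (5.2.2.3); about 40 per arm (8.1.3), so 40 - 8 = 32 after the lead-in; 80 patients in 1 year (8.1.4) or 3 years (1.0). **Assumptions.** True DLT rates p of 10-40%, independent patients, even accrual and a 50:50 split between arms.

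**Step 1, the rule as written.** P(pass) = P(X ≤ 2) with X ~ Binomial(8, p). At p = 0.4: 0.0168 + 0.0896 + 0.2090 = 0.315, so P(stop) = 0.685. If an arm passes at that rate, 32 × 0.4 = 12.8 further DLTs are expected with no numeric rule applied.

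**Step 2, the count continued.** An exact recursion carries the distribution of cumulative DLTs from look to look and removes the paths that reach a limit. Limits are written as DLTs/patients.

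| True DLT rate | Pass 8-patient rule | Stop: 3/8 only | Stop: 3/8, 6/16 | Stop: 3/8, 6/16, 8/24, 10/32 | Stop: 3/8, 5/16, 7/24, 9/32 |
|---|---|---|---|---|---|
| 10% | 96% | 3.8% | 3.9% | 4.0% | 4.9% |
| 20% | 80% | 20% | 22% | 26% | 36% |
| 30% | 55% | 45% | 52% | 67% | 78% |
| 40% | 32% | 68% | 79% | 93% | 97% |

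**Step 3, patients dosed when both lead-ins complete.**
- Time from the eighth patient's first dose: 1-3 weeks to surgery, 4-11 to the first adjuvant dose, 1 to radiation, about 6 of radiation, 4 of observation. Low end 1 + 4 + 1 + 6 + 4 = 16 weeks; high end 3 + 11 + 1 + 6 + 4 = 25 weeks.
- Expected registrations until each arm has 8 patients, at a 50:50 split: 19.1.
- Number dosed = 19.1 + monthly rate × weeks / 4.345.
- 1-year accrual (80/12 = 6.67 a month): 19.1 + 24.5 = 43.6 to 19.1 + 38.4 = 57.5, or about 44-58.
- 3-year accrual (80/36 = 2.22 a month): 19.1 + 8.2 = 27.3 to 19.1 + 12.8 = 31.9, or about 27-32.

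Table 2 places radiation 4-8 weeks after resection, which does not match 4-11 weeks to the first adjuvant dose plus one week. On Table 2 the high end is 3 + 8 + 6 + 4 = 21 weeks, or 19.1 + 32.2 = about 51 patients at 1-year accrual.

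**Step 4, which limits can act.** At 1-year accrual an arm enrols 40 patients in 52 weeks: the last 8 take 10.4 weeks and the last 16 take 20.8. Against a 16-25 week evaluation, the 32-patient limit would be fully evaluable only after accrual ends, and the 24-patient limit possibly so. At 3-year accrual (156 weeks) the last 8 take 31.2 weeks, so all limits can act.

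**The case against.** The strongest reply is that a short lead-in followed by DSMB oversight is a deliberate and internally consistent design. Much of that stands. A reader might infer that later DLTs have no consequence, or that a toxic combination passes unchecked. The documents do not support this: any DLT ends pembrolizumab in that patient, safety is monitored throughout (4.2.3.1), and the termination criterion and DSMB review cover the whole trial. What is missing is a number. Nor do the DSMB's listed inputs name DLT counts; because a DLT depends on attribution and treatment delay, tables of adverse event grades would not by themselves show it.

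A reader might also infer that enrolment cannot be stopped until the lead-in is complete. That is wrong too: review is rolling and a third DLT closes the arm at any time. The exposure figures are therefore upper figures. They also wait for both arms, though the rule works arm by arm, and include four weeks after radiation in which, by definition, no new DLT can arise (6.67 × 4 / 4.345 = about 6 patients at 1-year accrual).

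It might be tempting to say that all 80 patients could be dosed before the lead-in is complete. That needs the top of the per-site range in 8.1.4 (7 sites at 2 a month, 14 a month), faster than the plan's own 1-year forecast.

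Finally, the remedy has the same evaluation lag, and both the DLT rates and the example limits are the reviewer's. These points stand and are reflected in the ranges given.

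**Conclusion.** The point holds as a gap in pre-specification: after patient 8 in an arm, no numeric boundary applies to DLTs, and enrolment continues while the lead-in is pending. On its own the 8-patient rule lets true rates of 20%, 30% and 40% pass with probability 80%, 55% and 32% per arm. These probabilities are exact, but the rates are illustrative because the plan names none as unacceptable. The dosed-by-completion figures (44-58 or 27-32 of 80) are upper figures that rest on even accrual, an equal split and the stated treatment windows. The documents do not show that later patients are unprotected, and the design is not invalid. This is a low-cost improvement worth making.

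**What to change.** Keep the 8-patient rule. In Sections 5.2.2.3 and 8.2.1, continue the same DLT count for every later patient in each arm, with cumulative limits set in advance by the statistician and DSMB and applied on a rolling basis as each DLT occurs. Name the DLT count among the DSMB's inputs in 10.6.2, and say whether the existing provision for events before surgery carries over.

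As an example only, 6/16, 8/24 and 10/32 raise the stopping probability from 45% to 67% at a 30% rate and from 68% to 93% at 40% if all limits can act before accrual ends; if only the 8- and 16-patient limits can, the figures are 52% and 79%.

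Reconcile the 1-year and 3-year accrual figures, since they decide how many limits can act, and reconcile the two statements of time from surgery to adjuvant treatment.

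The cost is protocol wording and continuation of an existing review; DLT status already has to be judged for each patient under 5.2.2.3.1. The statistical price is more closures at tolerable rates: at a 20% rate from 20% to 26%, or about 36% with tighter limits of 5/16, 7/24 and 9/32; at 10%, from 3.8% to 4.0% with the example limits.

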### 2.1 Trial Design

This study will be a two arm phase II trial including 80 patients with head and neck squamous cell carcinoma (HNSCC) eligible for resection. Patients who are identified to be clinically high risk (see inclusion) prior to resection will be screened and consented to receive 1 dose Pembrolizumab followed by resection. Post-resection, patients will be stratified and if high risk features are confirmed by pathology (extracapsular extension [ECE], or positive margins), patients will receive concurrent weekly Cisplatin, daily radiation and every three week Pembrolizumab as shown in schema. If those enrolled prior to resection are found to not have high risk pathological features, they will go on to receive radiation and Pembrolizumab. Eight patients from each group will be enrolled as part of a lead-in on a rolling basis to determine the safety of this combination with stopping rules if expected toxicity is exceeded. There will be a fair proportion of patients who are identified to be high risk prior to resection but do not have confirmed high risk pathologic features. Therefore, we expect that using our criteria, that at least 50% (or 40 patients) will have high risk features requiring chemotherapy in addition to radiation (CRT) and Pembrolizumab while the remaining intermediate risk patients will receive radiation and Pembrolizumab. For correlative studies, archived or fresh biopsy samples and resection tissue will be assessed by H&E and IHC for immune phenotype. Blood samples will also be collected as described in section 7 for correlative studies. Patients will be followed approximately weekly during treatment,

then monthly for the first 3 months following treatment and then every 3 months thereafter for the first two years. A repeat PET/CT or CT scan will be performed at 3 months post-treatment to assess for early relapse. Patients will be assessed every 3 months for the first 2 years and then every 6 months for the next 3 years for disease free survival (DFS) and overall survival (OS).

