#### **5.2.2.3.1 Dose Limiting Toxicity**

Dose limiting toxicity will be defined as any adverse effect, that in the treating investigator’s opinion, was felt to be due to Pembrolizumab and significantly delayed standard of care treatment (> 7 days delay in surgery, >3 days for radiation, and/or >7 days for Cisplatin dose). In these patients, Pembrolizumab will be discontinued permanently.

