#### **5.3 Stratification**

After surgical resection, patients will be stratified into two groups: high risk patients with proven positive surgical margins or extracapsular extension of lymph nodes or intermediate risk including all patients not meeting criteria for high risk. There is a small chance that although patients are identified clinically to require radiation prior to surgery, that the pathology will deem the patient to be low risk and radiation would not be considered standard of care. In the event, the investigator feels it is not in the best interest of patient to administer radiation (or radiation would not be considered standard of care), then patient may be withdrawn from the study.

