### **5.8 Subject Replacement Strategy**

Patients who are unfit or unwilling to continue study after resection will be replaced. Patients who choose not to undergo surgical resection after initial dose of Pembrolizumab will be replaced. In addition, any patient who does not complete at least 1 week of adjuvant treatment will also be replaced.

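### The lead-in judges the common pre-surgery pembrolizumab dose by counts within arms assigned only after resection, so the decision can turn on how DLTs split between arms, and a DLT that prevents resection has no stated place in the count

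*Combined protocol and SAP*

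**What the plan says.** Section 5.2.2.3 makes the first eight patients of each arm the lead-in. Weekly calls review their DLTs "to evaluate the safety of the combination as well as the safety of administering Pembrolizumab before surgery". The stopping rule is ">2 out of the 8 patients in the safety cohort have developed a DLT, then no further patient may be enrolled to that arm". Section 4.2.3.1 repeats the same threshold per arm. One sentence then deals with the pre-surgery dose: "If the safety event occurs prior to surgery only, than the pre-surgery dose of Pembrolizumab will be discontinued for the following patients", with the trial continuing as adjuvant treatment only. No separate count or denominator is given for that decision, and 'the safety event' is not defined.

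Section 5.2.2.3.1 defines a DLT as a pembrolizumab-attributed effect that "significantly delayed standard of care treatment (> 7 days delay in surgery", or that causes set delays to radiation or cisplatin. A cancelled operation is not named.

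The arm is not known when the pre-surgery dose is given: "After surgical resection, patients will be stratified into two groups" (section 5.3). On replacement, section 5.8 says "Patients who choose not to undergo surgical resection after initial dose of Pembrolizumab will be replaced" and "any patient who does not complete at least 1 week of adjuvant treatment will also be replaced". It does not say whether replaced patients remain in the DLT count.

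**The concern.** The pre-surgery dose is one exposure, identical for everyone, and its risk is run before the arm exists. Counting its DLTs within arms formed later from pathology splits one question in two. The answer can then depend on margins and extracapsular extension, which say nothing about whether the dose delayed surgery.

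The second gap is more serious in kind. The patients are eligible for resection, so the worst pre-surgery outcome is an operation that never takes place. Such a patient is never assigned an arm and so belongs to neither group of eight. Followed literally, the only numeric rule can miss that event.

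**Working it through.** **Inputs.** From section 5.2.2.3: 8 patients per arm, 16 in all, with a trigger at 3 or more in one arm. From section 2.1: one pre-surgery dose for all patients, and "we expect that using our criteria, that at least 50% (or 40 patients) will have high risk features". The documents give no DLT rate, no fraction of DLTs that prevent resection, and no operating characteristics for the lead-in, so there is no plan figure to reproduce. The rates p and fractions q below are assumptions. Only pre-surgery DLTs are considered, with the same risk in both arms, and 'the safety event' is read as crossing the threshold unless stated.

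**1. Which splits trigger.** With k DLTs among 16 patients, P(a in one arm, k−a in the other) = C(8,a)·C(8,k−a)/C(16,k).

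- k = 3: only 3+0 and 0+3 trigger. 2·C(8,3)/C(16,3) = 112/560 = 20%.
- k = 4: only 2+2 fails to trigger. C(8,2)²/C(16,4) = 784/1820 = 43%, so 57% trigger.
- k ≤ 2 never triggers; k ≥ 5 always does.

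So 3 of 16 can drop the dose while 4 of 16 need not.

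**2. How much the split matters overall.** Current rule: 1 − P(Bin(8,p) ≤ 2)². Pooled rule: P(Bin(16,p) ≥ 4). A 2+2 split: P(Bin(8,p) = 2)². Using both triggers together adds only the 2+2 cases, so it equals the current rule plus the 2+2 column.

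| Assumed p | Current | Pooled 4 of 16 | 2+2 split | Both triggers |
|---|---|---|---|---|
| 5% | 1.2% | 0.7% | 0.3% | 1.4% |
| 10% | 7.5% | 6.8% | 2.2% | 9.7% |
| 20% | 36.5% | 40.2% | 8.6% | 45.1% |
| 30% | 69.6% | 75.4% | 8.8% | 78.3% |

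The last column assumes that the same 16 patients fill both counts.

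**3. DLTs that prevent resection.** If a fraction q of pre-surgery DLTs prevent resection, and those patients are replaced without being counted, the rate among counted patients is p(1−q)/(1−pq). The per-arm rule is held fixed:

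- p = 20%, q = 0.10: counted rate 0.1837; dropping falls from 36.5% to 30.8%.
- p = 20%, q = 0.25: counted rate 0.1579; falls to 22.4%.
- p = 30%, q = 0.10: counted rate 0.2784; falls from 69.6% to 63.2%.
- p = 30%, q = 0.25: counted rate 0.2432; falls to 51.7%.

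**4. The other reading.** If 'the safety event' means any single pre-surgery DLT, the reversal in step 1 disappears. The dose would then be dropped with probability 1 − 0.95^16 = 56% at a 5% rate and 1 − 0.90^16 = 81% at 10%.

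**5. Sequential accrual.** At 50% high risk, filling both eights takes 19.1 dosed patients on average, and exactly 16 suffice in about 20% of trials. Simulated on that basis, both triggers together drop the dose in about 10% of trials at a 10% rate and 47% at 20%.

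**The case against.** The best case against has four parts.

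First, the reversal depends on one reading of an undefined term. That is correct. The threshold reading is the natural one, because the sentence follows directly on the >2 of 8 rule, but it remains a reading. The unresected-patient gap does not depend on it.

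Second, the split effect is close to a wash. Current and pooled rules differ by at most about 6 percentage points at the rates tabulated, and at 10% or below the current rule stops slightly more often. That stands, and it rules out calling the current rule markedly less protective on this ground.

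Third, other safeguards exist. Section 5.2.2.3 has weekly calls, section 5.9 allows termination for adverse reactions, and section 7.2.3.1 requires serious events to reach the sponsor within 24 hours. Section 8.2.3.1 keeps patients who received only pre-resection pembrolizumab in the safety analysis, and section 10.6.2 provides a DSMB. These make it unlikely that a cancelled operation would go unnoticed. None supplies a count for such a patient, and the DSMB is advisory.

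Fourth, replacing the per-arm trigger with a pool of 16 could do harm. Suppose the first 16 dosed are 11 high risk and 5 intermediate, with 3 pre-surgery DLTs among the first eight high-risk patients, and patients 17 to 19 are intermediate and all have one. A pool closed at 16 holds 3 DLTs and does not act, although 6 of 19 patients have had one; the current rule drops the dose. This is a sound reason to add a pooled trigger and keep the per-arm one.

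**Conclusion.** The concern holds in a limited form. A dose common to all patients is judged within arms that do not exist when it is given. On the natural reading, 3 of 16 DLTs can end it while 4 of 16 need not. On either reading, a patient whose DLT prevents resection has no arm in which to be counted.

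The split effect alone is modest. Uncounted events could matter more: at an assumed 20% rate, the chance of dropping the dose falls by about 6 points if a tenth of DLTs prevent resection, or 14 if a quarter do. Those figures rest on assumed rates and on the further assumption that such patients are left out. The structural gap rests on neither.

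A reader might infer more in two ways. One is that the protocol removes these patients' DLTs. Section 5.8 replaces patients but is silent on their events, so the fault is an omission. The other is to set 22% under the per-arm rule with missed events against 40% under a pooled rule with none missed. That comparison adds two separate effects; the like-for-like fall is from 36% to 22%.

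**What to change.** Amend section 5.2.2.3 as follows:

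- (a) Define 'the safety event' as crossing the threshold. Count as a pre-surgery DLT any pembrolizumab-attributed event that delays surgery by more than 7 days or prevents it.
- (b) Keep the per-arm trigger, including dropping the pre-surgery dose when an arm exceeds 2 of 8 with pre-surgery DLTs only.
- (c) Add a trigger that also drops the pre-surgery dose at 4 or more pre-surgery DLTs among the first 16 dosed patients, regardless of later arm, resection or replacement.
- (d) State that replaced patients stay in the count: their DLTs remain counted, and their replacements are still observed.

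Because (c) is added to (b), no case that stops now on the threshold reading would go unstopped.

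The cost is a few sentences, with no extra patients, visits or data. The pooled count is complete once surgery for the 16th dosed patient has taken place or been ruled out, without waiting for both arms to fill. The downside is slightly more stopping at low rates: from 7.5% to 9.7% at a 10% rate and from 36% to 45% at 20% if the same 16 patients fill both counts, or to about 10% and 47% with sequential accrual at 50% high risk. If the lead-in is already complete, the sponsor should state how pre-surgery and unresected DLTs were counted.

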#### **5.2.2.3.1 Dose Limiting Toxicity**

Dose limiting toxicity will be defined as any adverse effect, that in the treating investigator’s opinion, was felt to be due to Pembrolizumab and significantly delayed standard of care treatment (> 7 days delay in surgery, >3 days for radiation, and/or >7 days for Cisplatin dose). In these patients, Pembrolizumab will be discontinued permanently.

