Nausea and Vomiting: Maximum supportive therapy will be given, and Cisplatin will be continued at full dose for  $\leq$  grade 2 nausea and vomiting. For grade 3 nausea and vomiting refractory to supportive therapy, Cisplatin will be held until recovery to < grade 2. No dose reductions will be made.

Mucositis: Significant mucositis (grade 3-4, CTCAE, v. 4) is expected from radiation and Cisplatin and should not be a reason for a treatment break, unless it significantly interferes with fluid intake or nutrition. Aggressive supportive care is encouraged as well as consideration of a PEG tube if not already

done.

Ototoxicity: For clinical hearing loss not requiring a hearing aid, reduce Cisplatin by 2 dose levels (23mg/m^2). For hearing loss requiring a hearing aid, discontinue Cisplatin. For grade 2-3 tinnitus (CTCAE, v. 4) at the time of retreatment, hold Cisplatin until improvement to grade 1 or less and then reduce the following doses of Cisplatin by 2 dose levels. If tinnitus does not improve to grade 1 or less by the last day of radiation therapy, discontinue Cisplatin. An audiogram is recommended when there is any report of significant change in hearing and/or an increase in tinnitus.

Other Toxicities: For any other grade 3-4 adverse events, hold Cisplatin until toxicities have recovered to grade 1 or less. Dose may be reduced by 1 or 2 dose levels for next treatment if felt necessary by discretion of investigator.

If any doses of Cisplatin are skipped due to hematologic, neurologic, renal, or other adverse events, these doses will NOT be made up at end of treatment. Cisplatin will continue only during time of radiation treatment. If a weight change of  $\geq 10\%$  occurs, the following Cisplatin doses should be adjusted.

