The assessment of relationship will be reported on the case report forms /worksheets by an investigator who is a qualified physician according to his/her best clinical judgment, including consideration of the above elements.		
Record one of the following	Use the following scale of criteria as guidance (not all criteria must be present to be indicative of a Merck product relationship).	

Yes, there is a reasonable possibility of Merck product relationship.	There is evidence of exposure to the Merck product. The temporal sequence of the AE onset relative to the administration of the Merck product is reasonable. The AE is more likely explained by the Merck product than by another cause.
--	--

No, there is not a reasonable possibility Merck product relationship	Subject did not receive the Merck product OR temporal sequence of the AE onset relative to administration of the Merck product is not reasonable OR there is another obvious cause of the AE. (Also entered for a subject with overdose without an associated AE.)
---	--

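### The lead-in stopping count takes only delays attributed to pembrolizumab, while the protocol's rationale states the criterion without attribution; the attributed count has low sensitivity to worsened chemoradiation toxicity

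*Combined protocol and SAP*

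**What the plan says.** **The count.** Under section 5.2.2.3.1 an adverse effect is a DLT when, in the treating investigator's opinion, it "was felt to be due to Pembrolizumab and significantly delayed standard of care treatment". The limits are "> 7 days delay in surgery, >3 days for radiation, and/or >7 days for Cisplatin dose". The same section attaches a patient-level instruction on pembrolizumab to each DLT.

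**The decision.** Section 5.2.2.3 has weekly calls on the first eight patients in each arm, "to evaluate the safety of the combination as well as the safety of administering Pembrolizumab before surgery". The boundary is met when "safety analysis reveals >2 out of the 8 patients in the safety cohort have developed a DLT". The stated consequence is that "no further patient may be enrolled to that arm due to excess toxicity with this combination". Enrolment continues beyond the eighth patient while this is assessed.

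**The rationale.** Section 4.2.3.1 lets the trial proceed provided standard therapy is not significantly affected, which it glosses as a delay in more than 2 of 8 patients per arm. It names no cause. The first hypothesis in section 3.1 likewise speaks of little interruption to standard therapy, without attribution.

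**Guidance on cause.** Table 6 in section 7.2.4 is a yes/no scale. Among the criteria for yes is "The AE is more likely explained by the Merck product than by another cause"; among those for no is "there is another obvious cause of the AE". It has no category for an event to which pembrolizumab contributed. Section 5.2.2.4.2 says "Significant mucositis (grade 3-4, CTCAE, v. 4) is expected from radiation and Cisplatin", and section 4.2.3.1 describes pembrolizumab's toxicities as different in kind from those of radiation and chemotherapy.

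**The concern.** A new drug added to chemoradiation can do harm in two ways. It can cause its own recognisable events, such as immune-related ones, or it can make familiar events (mucositis, dermatitis, renal or marrow toxicity) more frequent or more severe. The first kind can be judged patient by patient. The second usually cannot: one patient with a radiation break for severe mucositis looks the same with or without pembrolizumab, and the excess shows only in the rate.

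A count that requires attribution is therefore suited to the first kind and insensitive to the second, yet section 5.2.2.3 reads the result as a statement about the combination. Because section 4.2.3.1 carries no attribution condition, a reader cannot tell which count will be reported as the lead-in result. At stake is what a passed lead-in means, and how soon more frequent interruption of radiation or cisplatin would be noticed while enrolment stays open.

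**Working it through.** **Inputs from the documents.** Eight lead-in patients per arm; closure at more than 2, that is 3 or more (section 5.2.2.3); attribution required (section 5.2.2.3.1). The documents give no operating characteristics for this rule, no background delay rate and no attribution share, so there is no stated figure to reproduce.

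**Assumed inputs.** Background rate *b* of adverse-event delays beyond the limits: 20%. Rate with pembrolizumab *q*: 50%. Share *s* of the excess delays that investigators attribute to pembrolizumab: 25%, 50% or 100%. Patients are independent, and no background delay is attributed to pembrolizumab.

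**Formula.** Counted rate p = s × (q − b). Firing probability P(X ≥ 3) = 1 − [(1−p)^8 + 8p(1−p)^7 + 28p²(1−p)^6]. The count can only rise, so reviewing it on a rolling basis does not change this probability.

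**Results for an excess of 50% − 20% = 30 points.**

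| What is counted | p | P(3 or more of 8) |
|---|---|---|
| A quarter of the excess | 0.25 × 0.30 = 0.075 | 1.8% |
| Half of the excess | 0.50 × 0.30 = 0.15 | 10.5% |
| All of the excess | 0.30 | 44.8% |
| All adverse-event delays | 0.50 | 85.5% |

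Worked line for p = 0.15: 0.2725 + 0.3847 + 0.2376 = 0.8948, so the probability is 1 − 0.8948 = 10.5%.

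**A different attribution model.** If investigators attribute a fixed share of all delays, background included, then at q = 50% a share of one half gives p = 0.25 and a probability of 32.1%; a share of one quarter gives p = 0.125 and 6.7%.

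**The price of an all-cause count.** With no pembrolizumab effect, 3 or more of 8 is reached by background delays alone with these probabilities:

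| Background rate | Per arm | At least one of two arms |
|---|---|---|
| 10% | 3.8% | 1 − 0.962² = 7.5% |
| 20% | 20.3% | 1 − 0.797² = 36.5% |
| 30% | 44.8% | 1 − 0.552² = 69.5% |

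The attributed deaths of sensitivity and the all-cause false triggers thus both depend on rates that the plan does not state. What needs no assumption is the direction: attributed delays are a subset of all adverse-event delays, so the attributed count can never reach 3 before the all-cause count does.

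**The case against.** The strongest reply is that attribution is a deliberate trade-off. Head and neck chemoradiation is toxic by itself, and a rule that closed an arm on any three delays could stop a harmless combination; at a 30% background it would do so 44.8% of the time. That stands, and it is a reason not to turn the all-cause count into an automatic closure rule.

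The 85.5% comparator is also generous, because it includes background delays. Even perfect attribution of a 30-point excess fires only 44.8% of the time, so part of the gap comes from counting the background, and the small sample limits any version. This stands too.

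A reader might infer that Table 6 obliges investigators to assign expected toxicity to radiation or cisplatin. The text does not go that far. The table names neither treatment, describes itself as guidance, defers to clinical judgement, and also weighs time course, dechallenge and rechallenge. Section 5.2.2.3.1 does not refer to it. The mucositis sentence in section 5.2.2.4.2 goes on to say that mucositis should not lead to a break unless intake or nutrition suffers. These passages point investigators away from attribution; they do not dictate it.

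Other safeguards carry no attribution condition. Sections 8.1.1 and 8.2.4.1 compare adverse event rates with historical targets (50% and 39% for grade 3 and 4 events). The DSMB receives adverse event frequency and severity (section 10.6.2). Section 7.1.1.7 requires sponsor consultation for longer radiation delays or more than two skipped cisplatin doses. Section 5.9 allows termination on the incidence or severity of adverse drug reactions. They soften the concern, but none sets a numerical boundary for lead-in delays, and the historical comparison concerns grade and not delay.

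Finally, section 4.2.3.1 may be only shorthand for the fuller definition. That is possible, but the text does not say so.

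**Conclusion.** The point holds in a limited form. Sections 4.2.3.1 and 5.2.2.3.1 state the lead-in criterion differently on attribution, and the version that would be applied has low sensitivity to pembrolizumab worsening ordinary chemoradiation toxicity, although its result is read as a verdict on the combination. That conclusion rests on the text and on the subset argument. The size does not: 1.8%, 10.5% and 44.8% against 85.5% follow from an assumed rise from 20% to 50% and assumed attribution shares.

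A reader might go further and infer that the rule is almost blind, or could never fire. The documents do not support that. Delays from clearly immune-related events would still count, and the rule fires 10.5% of the time at half attribution of the assumed excess and 44.8% at full attribution. Near-blindness would require shares of about a quarter or less, and the plan gives no share. Nor do the documents say that the safety hypothesis in section 3.1 will be judged on the DLT count; the safety endpoints are all graded adverse events.

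This is a cheap improvement to what the lead-in can show. It does not invalidate the lead-in.

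**What to change.** 1. Reconcile sections 4.2.3.1 and 5.2.2.3.1, so that one criterion, with or without attribution, is stated in both. Which closure rule applies, and the patient-level instruction in 5.2.2.3.1, are for the sponsor to decide.
2. Add to section 5.2.2.3 a second count for each arm: lead-in patients whose surgery, radiation or cisplatin was delayed beyond the limits already stated in 5.2.2.3.1 by any adverse event, whatever its attribution.
3. Review this count on the existing weekly calls, send it to the DSMB, and report it with an exact 95% CI beside the attributed DLT count.
4. If a numerical trigger for DSMB review is attached, state the assumed background delay rate and the resulting false-trigger probability. For 3 or more of 8 this is 3.8%, 20.3% or 44.8% per arm at backgrounds of 10%, 20% or 30%. Without a stated background the trigger is uncalibrated.

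The cost is a short paragraph, one extra tabulation and an occasional unneeded DSMB discussion. Radiation breaks and their reasons must already be recorded (section 5.2.2.2.7, Compliance Criteria). Keeping the new count separate from the DLT definition leaves treatment rules and delay limits unchanged.
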